5.2 EXCLUSION CRITERIA

An individual who meets any of the following criteria will be excluded from participation in this study:

- 1. Current or prior history of any of the following:
 - a. Clinically significant illness (other than HIV) or any other major medical disorder that may, in the opinion of the investigator, interfere with the subject treatment, assessment of compliance with the protocol; subjects currently under evaluation for a clinically-significant illness (other than HIV) are also excluded
 - b. Poor venous access interfering with required study blood collection
 - c. Solid organ transplantation
 - d. Significant pulmonary disease, significant cardiac disease, or porphyria
 - e. Uncontrolled chronic hepatitis B infection (surface antigen positive with detectable HBV DNA as noted in patient's medical documentation from a treating physician)
 - f. Chronic hepatitis C infection (current active only)
 - g. Unstable psychiatric disease. (Subjects with psychiatric illness that is well-controlled on a stable treatment regimen or currently not requiring medication may be included.)
 - h. Any malignancy or its treatment that in the opinion of the PI may cause ongoing interference with host immunity; subjects under evaluation for malignancy are not eligible.
- 2. Abnormal hematological and biochemical parameters at screening, unless the test has been repeated and at least one subsequent result is within the acceptable range prior to study drug administration, including:
 - a. Neutrophil count <750 cells/mm³
 - b. Hemoglobin level <10 g/dL
 - c. Platelet count ≤50,000 cells/mm³
 - d. Estimated glomerular filtration rate, calculated by the chronic kidney disease epidemiology collaboration formula: <30 mL/min/1.73 m²
 - e. ALT or AST level ≥5 times upper limit of normal (ULN)
 - f. Total bilirubin level ≥2.0 times ULN, except in subjects with Gilbert's syndrome or other clinical explanation at the discretion of the PI
 - g. Albumin level <3 g/dL
- 3. Poorly controlled diabetes as indicated by a screening glycosylated hemoglobin (HbA1c) >10
- 4. Need for the use of the following medications from 21 days prior to the start of study drugs through the end of treatment:
 - a. Hematologic stimulating agents, erythropoiesis stimulating agents (ESAs), granulocyte colony stimulating factor (GCSF, thrombopoietin (TPO) mimetics

- b. Chronic systemic antineoplastic or immunomodulatory treatment including supraphysiologic doses of immunosuppressants such as corticosteroids (e.g., prednisone equivalent >10 mg/day for >2 weeks), azathioprine or monoclonal antibodies (e.g., infliximab)
- c. Investigational agents or devices for any indication
- 5. Hyperlipidemia (defined as an LDL≥190 mg/dL), that is not being treated per the 2018 ACC/AHA Cholesterol Clinical Practice guidelines with medications such as statins, Ezetimibe, and PCSK9 inhibitors, since these would be the standard of care for these patients., Patients with hyperlipidemia who are deemed ineligible to be on statin therapy by a treating physician will not be excluded.
- 6. Initiation of statin therapy or change in dose of already-prescribed statin therapy within the last 3 months.
- 7. Known history of cardiac arrhythmia or baseline ECG with arrhythmia including but not limited to atrial fibrillation (with or without rapid ventricular rate), supraventricular tachycardia or ventricular tachycardia.
- 8. Any medical, psychiatric, social condition, occupational reason or other responsibility that, in the judgment of the investigator, is a contraindication to protocol participation or impairs a volunteer's ability to give informed consent.

Female-specific criteria:

9. Woman who is breast-feeding or planning to become pregnant during the first 24 weeks after study drug administration.

5.3 LIFESTYLE CONSIDERATIONS

During this study, participants are asked to:

- Abstain from alcohol for 24 hours before the start of each dosing session until after collection of the final PK and/or pharmacodynamic sample. If participants do not abstain from alcohol use, samples will not be collected for PK assessment. This will be pertinent for 6 subjects in the study.
- Fasting prior to blood draws for each study visit.
- If having FDG-PET/CT, nothing by mouth for 6 hours prior to the imaging study. This will be pertinent for 12 subjects in the study. Subjects should dress in warm, comfortable clothing with no zippers, snaps clips or metal of any kind. A high fat/low carbohydrate diet should be followed for 24 hours prior to the imaging study.

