3.1.2 SECONDARY OBJECTIVES

To evaluate the effect of CD24Fc on the following variables between the placebo and intervention arms in comparison with baseline values:

- 1. Levels of total cholesterol, HDL, and triglycerides
- 2. Markers of immune activation (CD4 and CD8 T cells, IFN, TNF, sCD14)
- 3. Size of HIV reservoirs
- 4. Myocardial damage (measured by Troponin I and T)
- 5. Hepatic steatosis, as determined by transient elastography
- 6. Leptin
- 7. Hemoglobin A1c

- 8. Presence of anti-drug antibody (ADA) and temporal correlation to any adverse events, and its effect on PK (For first 6 subjects).
- 9. The pharmacokinetics (PK) and pharmacodynamics (PD) of CD24Fc in the first 6 randomized subjects.
- 10. Changes in IL-6, apoB, Lp(a), urine albumin to creatinine ratio before and after treatment.

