6.3 MEASURES TO MINIMIZE BIAS: RANDOMIZATION AND BLINDING

This is a randomized, double-blinded, placebo-controlled trial. Subjects will be randomized using block randomization in a 1:1 ratio of CD24Fc:placebo. They will be block randomized in blocks of six (except for the last block of four). The first block of six will all have PK analyses and there will be a safety and efficacy review upon completion of dosing by this group of six without halting enrollment.

Every effort will be made to minimize the various known sources of bias. Breaking the blind will be considered only when knowledge of the treatment assignment is deemed essential by the subject's physician for the subject's care. Any intentional or unintentional breaking of the blind will be reported to the sponsor and IRB, and explained at the end of the trial, irrespective of the reason for its occurrence.

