- Lipid Panel- serum (fasting). This assay will be done through LabCorp. This test includes Cholesterol, total; high-density lipoprotein (HDL) cholesterol; low-density lipoprotein (LDL) cholesterol (calculation); triglycerides; very low-density lipoprotein (VLDL) cholesterol (calculation).
- Hepatitis B panel- HBV Evaluation Panel, serum or plasma. This assay will be done through LabCorp. This test includes Hepatitis B core antibody, total; hepatitis B surface antibody, qualitative; hepatitis B surface antigen
- Hepatitis C Ab with reflex RNA- Hepatitis C Virus (HCV) Antibody with reflex to quantitative realtime PCR, serum or plasma. This assay will be done through LabCorp.
- Serum hCG- human chorionic gonadotropin, beta-subunit, qualitative, serum. This assay will be done through LabCorp. A serum hCG will be done for females of child-bearing potential, at the screening visit.
- Urine hCG- human chorionic gonadotropin, beta-subunit, qualitative, urine. This will be a pointof care assay. A urine hCG will be done for females of child-bearing potential before drug dosing, using a point-of-care urine hCG assay.
- Troponin I and T- In conjunction of cardiovascular inflammation measurement, we will also assess myocardial damage using a validated, sensitive cardiac troponin I and T assays (through LabCorp) will be used for all subjects run as batched samples.

- Leptin- serum or plasma (fasting). Used as a marker for lipodystrophy.
- hsCRP (high-sensitivity CRP), serum or plasma. This assay will be done through LabCorp.
- IL-6 (Interleukin- 6), serum or plasma.
- Apo B (apoliprotein B), serum. This assay will be done through LabCorp.
- Lp(a) (Lipoprotein a), serum. This assay will be done through LabCorp.
- Urine albumin /creatinine ratio, random urine. This assay will be done through LabCorp.
- Pharmacokinetic analyses- done for the first 6 subjects receiving CD24Fc.
 For PK analysis, blood samples will be collected prior to drug infusion at weeks 0, 2, 4, 6, 16, 28 before and 2 hours post dosing of CD24Fc as applicable. A +-/10-minute window around each draw point will be allowed. At weeks 6 and 28, a blood sample for PK will also be collected in order to demonstrate a decrease in drug concentration after dosing completion on week 4.

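### Section 5.3 leaves PK samples undrawn after alcohol use, without a stated reason, in a subset with as few as 3 CD24Fc recipients

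*Combined protocol and SAP*

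**What the plan says.** The request in section 5.3 (Lifestyle Considerations) reads: "Abstain from alcohol for 24 hours before the start of each dosing session until after collection of the final PK and/or pharmacodynamic sample". The consequence follows: "If participants do not abstain from alcohol use, samples will not be collected for PK assessment". On scope, the section adds: "This will be pertinent for 6 subjects in the study".

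Three other parts of the protocol determine how much this costs.

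- **Who has PK.** Section 6.3 states "Subjects will be randomized using block randomization in a 1:1 ratio of CD24Fc:placebo", with blocks of six, and then "The first block of six will all have PK analyses". Section 3.1.2 agrees and lists as a secondary objective "The pharmacokinetics (PK) and pharmacodynamics (PD) of CD24Fc in the first 6 randomized subjects". The PK entry in section 8.2, however, assigns the analyses to the first six people who receive CD24Fc.
- **What is sampled.** The Schedule of Activities (section 1.3) lists PK of both ART and CD24Fc. Samples are taken before and 2 hours after each dose at Day 0, Week 2 and Week 4, and once at each of Weeks 6, 16 and 28. Section 8.2 explains the late samples: "At weeks 6 and 28, a blood sample for PK will also be collected in order to demonstrate a decrease in drug concentration".
- **What else happens at the visit.** Sections 8.1.1.5 and 8.1.1.6 make the Week 2 and Week 4 infusions conditional on laboratory findings and adverse events; alcohol is not mentioned. The Schedule of Activities has safety, lipid and immunology bloods at every dosing visit. Section 7.2 does not replace participants who leave after receiving study drug. No section provides for a repeat PK draw or a substitute PK participant.

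**The concern.** The rule makes a PK value missing because of the participant's behaviour, and does so at the point of collection. A sample that is drawn and flagged can later be excluded, included, or used to see whether alcohol made a difference. A sample that is never drawn allows none of these. Since the visit, the dose and the other blood draws go ahead, the rule saves little and leaves a dosed participant's exposure unknown.

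The data at risk are few. They serve the secondary PK objective and the evaluation of the effect of anti-drug antibodies on PK. With 3 CD24Fc recipients, losing one at a timepoint leaves two values, from which a mean can hardly be estimated.

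**Working it through.** **The plan's own figure.** The documents give no sample-size or precision calculation for the PK subset. The trial's sample size (section 9.2: difference 15, SD 20, two-sided 0.05, 80% power) reproduces:

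- 2 × [20 × (1.960 + 0.842) / 15]² = 27.9, so 28 per arm
- 28 / 0.89 = 31.5, so 32 per arm and 64 in total

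The PK rule does not touch this figure.

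**Size of the PK subset.**

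- First block of six at 1:1 (sections 3.1.2 and 6.3): 6 × 1/2 = 3 on CD24Fc
- First six receiving CD24Fc (section 8.2): 6 on CD24Fc
- Scheduled samples per person: 3 × 2 + 3 = 9, so 27 or 54 from CD24Fc recipients

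The Day 0 pre-dose sample precedes any drug, so for CD24Fc it is a baseline value and not a trough. That leaves 8 post-exposure samples per person.

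**Loss from one skipped dosing visit.**

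| | 3 on CD24Fc | 6 on CD24Fc |
|---|---|---|
| Share of that visit's CD24Fc samples | 2/6 = one third | 2/12 = one sixth |
| Share of all scheduled samples from CD24Fc recipients | 2/27 = 7.4% | 2/54 = 3.7% |

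**Precision at one timepoint.** The 95% half-width for a mean, in SD units, is t(0.975, n−1)/√n:

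- n = 3: 2.48
- n = 2: 8.98
- n = 6: 1.05
- n = 5: 2.776/√5 = 1.24

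Losing one of three multiplies the half-width by 8.98/2.48 = 3.6. Losing one of six multiplies it by 1.24/1.05 = 1.2.

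**Chance and expected amount of loss.** The documents give no lapse rate. Let p be an assumed chance of a lapse per dosing visit. With 3 recipients there are 3 × 3 = 9 dosing visits and 18 dosing-visit samples. If lapses are independent, the chance that nothing is lost is (1−p)⁹. If instead the same people lapse every time, it is (1−p)³. The expected loss is 18p either way.

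| p | No loss, independent | No loss, same people each time | Expected loss of 18 samples |
|---|---|---|---|
| 5% | 63% | 86% | 0.9 (5%) |
| 10% | 39% | 73% | 1.8 (10%) |
| 20% | 13% | 51% | 3.6 (20%) |

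With 6 recipients there are 18 dosing visits. The independent no-loss chances are then (1−p)¹⁸ = 40%, 15% and 2%, but each loss matters less, and the expected share lost is unchanged.

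**The case against.** The best defence is that this is a small descriptive subset with no stated precision target, that the sponsor may have a reason for the rule, and that the expected loss is modest. Participants are asked to abstain, receive visit reminder calls and extra payment for PK visits (section 5.5), and dosing visits have a 4-day window either way (section 8.1) that leaves room to reschedule. All of this is fair. It lowers the likely lapse rate and limits the weight of the point. It does not explain why a sample should go undrawn once the participant has been dosed.

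A reader might infer more than the documents support:

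- **That the rule is needless because alcohol cannot affect an infused fusion protein.** The documents do not say so, and the PK panel also includes ART. The missing rationale supports asking for one, not declaring that none exists.
- **That only 3 people carry CD24Fc.** Section 8.2 implies 6, and the conflict is unresolved.
- **That participants must abstain until Week 28.** The final sample in section 5.3 could be the last of the study, but the 24-hour lead-in before each session points at least as well to the last sample of that session. This is an ambiguity, and the loss calculation above counts dosing visits only.
- **That one lapse ends a participant's PK sampling.** Sections 8.1.1.5 to 8.1.1.9 describe the PK group as those sampled at earlier visits. That reads as description; section 5.3 does not remove a whole profile.
- **That PD and anti-drug antibody data are lost too.** Non-collection is limited to PK assessment; those other draws continue.

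**Conclusion.** The point holds as a modest, inexpensive improvement. Section 5.3 turns an alcohol lapse into an unrecoverable PK gap, with no stated reason and no backup, in a subset of 3 or 6 CD24Fc recipients. A skipped dosing visit costs one third or one sixth of that visit's CD24Fc PK data. How often this would happen cannot be known from the documents: the 5%, 10% and 20% lapse rates are assumptions, and the 63%, 39% and 13% chances of no loss also assume independent lapses among 3 recipients. Collect-and-flag does not depend on those rates or on whether alcohol matters for either analyte, because it keeps every analysis option open. The primary LDL and safety endpoints, the sample size of 64, and the PD and anti-drug antibody draws are unaffected.

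**What to change.** 1. Keep the abstention request in section 5.3, but replace the non-collection sentence with: *PK samples (CD24Fc and ART) are collected whether or not the participant abstained; alcohol use in the preceding 24 hours is recorded, and PK results are shown with and without flagged samples.* If the sponsor prefers to keep the present rule, its rationale should be stated.
2. State whether the final PK or pharmacodynamic sample in section 5.3 is the last of that dosing session or of the study. This review does not prescribe which.
3. Reconcile sections 3.1.2 and 6.3 with section 8.2 on whether the PK subset is the first six randomized or the first six receiving CD24Fc.

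The cost is a few sentences and one case report form field; the visits and draws are already scheduled. There is a small downside: the change removes the only stated consequence of not abstaining.

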5.4 SCREEN FAILURES

Screen failures are defined as participants who consent to participate in the clinical trial but are not subsequently randomly assigned to the study intervention or entered in the study. A minimal set of screen failure information is required to ensure transparent reporting of screen failure participants, to meet the Consolidated Standards of Reporting Trials (CONSORT) publishing requirements and to respond to queries from regulatory authorities. Minimal information includes demography and the description of eligibility criteria failure.

Individuals who do not meet the criteria for participation in this trial (screen failure) because of an abnormal hematological or biochemical parameter, poorly controlled diabetes, or use of a restricted

medication (for example, exclusion criteria 4) may be rescreened. Rescreened participants should be assigned the same participant number as for the initial screening.

5.5 STRATEGIES FOR RECRUITMENT AND RETENTION

The study will be advertised and posted using flyers and the IHV website. All advertisements will be IRB approved before use. We will recruit patients from the University of Maryland Medical Center (UMMC) and from Unity Parkside Clinic in Washington DC (patients will only be seen at University of Maryland Medical Center). Recruitment of patients will take place largely from outpatient clinics at UMMC and Unity Parkside, where HIV patients are seen for primary care. A primary care physician may refer patients to the study team, in which case the study team will speak to the patient either in person or by phone to schedule a screening appointment at UMMC. Residents of DC will be provided transportation to UMMC via mileage reimbursement for Metro, train, Uber or driving as approved by the Sponsor or will be scheduled with transportation for the visit as needed.

Study retention will be promoted by visit reminders via phone calls. Participants will receive remuneration for their time and any inconvenience due to participating in the study (as outlined below).

An anticipated 110 subjects with HIV will be screened for this study (which includes screening failures and those lost to follow-up) in order to enroll 64 subjects.

This study will be limited to adults age 50 and older. This criterion has been included in order to study the effects of CD24Fc in a population with inherently higher CVD risk than those aged 18-49 years. Children and pregnant women will be excluded since the safety and efficacy of CD24Fc has not been studied in the pediatric population or during pregnancy. Any woman of child-bearing potential must have a negative serum pregnancy test prior to receiving the first dose of CD24Fc on Day 0 and use effective contraception throughout the study.

Subjects will not be excluded based on gender. This study is designed to target an underrepresented demographic of the HIV epidemic in the United States with poor representation in clinical trials, and in which current therapy is underutilized and has had poor results.

All remuneration made by the University of Maryland, Baltimore will be provided to participants for their time and inconvenience, as outlined below.

Screening Visit	\$50
FDG-PET/CT (#1) if applicable*	(\$200 if applicable)
Fasting Labs & Fibroscan (if needed, not included in totals below)	(\$25 if needed)
Day 0 Study Drug or Placebo Infusion	\$150 (+/- PK \$25)
Week 2 Study Drug or Placebo Infusion	\$150 (+/- PK \$25)
Week 4 Study Drug or Placebo Infusion	\$150 (+/- PK \$25)
Week 6 Follow up	\$50 (+/- PK \$25)
Week 16 Follow Up	\$50 (+/- PK \$25)

Week 28 Follow Up	\$50 (+/- PK \$25)
FDG-PET/CT (#2) if applicable*	(\$200 if applicable)
TOTAL	\$650
Additional for PK	\$150
Additional for FDG-PET/CT x2 at NIH	\$400
Additional if Fasting Screening labs / FibroScan Visit needed or when	\$25
unexpected visits are required	

*Compensation due for Optional FDG-PET/CT will be provided to subjects upon next visit to IHV and not at the NIH visit.

6 STUDY INTERVENTION

6.1 STUDY INTERVENTION(S) ADMINISTRATION

6.1.1 STUDY INTERVENTION DESCRIPTION

CD24Fc (CD24 Ig) is a fusion protein consisting of the extracellular domain of mature human CD24 linked to the human immunoglobulin G1 (IgG1) Fc domain. The complete molecular formula of CD24Fc has not been determined at this time. The mature protein is 261 amino acids long and each CD24Fc molecule includes the 30 amino acid CD24 extracellular domain. CD24Fc forms a disulfide-linked homodimer with a predicted mass of 57.7 kilodaltons (kDa) based on the homodimer amino acid sequence. However, the apparent molecular weight of the intact dimer is approximately 80 KDa based on non-reduced SDS-PAGE. The CD24 domain is highly glycosylated with both N-linked and O-linked oligosaccharides, which comprise approximately 80% of the mass of the CD24 domain.

For more information on the description of CD24Fc, please see section 3 of the IB.

6.1.2 DOSING AND ADMINISTRATION

Dosing of CD24Fc (240mg) will occur intravenously and over the duration of 1 hour (at minimum). A predose ECG will be completed prior to dosing. The IV rate may be reduced to prolong the duration of infusion at the discretion of the investigator and clinical team based upon symptoms suggestive of an infusion-related reaction. If an infusion reaction is deemed severe (e.g. severe hypotension, hypoxemia) the infusion will be stopped and assessment of AEs will proceed as outlined in section 8.

All enrolled subjects who have received CD24Fc will be evaluated for safety before and after dosing. Safety may be assessed by physical examination, vital signs, hematology, and/or chemistries (see section 8 for detailed study assessments and procedures per visit). Subjects do not have to be fasting to receive the infusion (but will be fasting to have lipid panel and leptin drawn, as specified in the SOA). Vital signs will include pulse, blood pressure, respiratory rate, and oxygen saturation. The severity of signs, symptoms, and AEs will be determined by using DAIDS toxicity table. Subjects will be monitored during the infusion and until 2 hours after the infusion has completed, with vital signs every 30 minutes (+/- 5

minutes with +/-10 minutes at 2 hours post) and a post-infusion ECG at two hours post dose (+/- 10 minutes). Laboratory results will be ascertained as needed based on reported symptoms. Please note that dose modifications will not be made.

6.2 PREPARATION/HANDLING/STORAGE/ACCOUNTABILITY

6.2.1 ACQUISITION AND ACCOUNTABILITY

The site will receive individual vials of CD24Fc (each shipment will consist of 8 vials of investigational product). Upon receipt of the investigational product, contents will be examined for damage or missing vials. The product will be immediately stored in the appropriate temperature-controlled conditions. Included in the shipment is a temperature monitoring device which will be used to verify the minimum and maximum temperatures reached. The Investigational Product Receipt Confirmation Form included with the shipment will be completed and returned to product Receipt of the shipment. If the device shows an out-of-range value, the drug will be quarantined within the appropriate temperature-controlled environment and the Temperature Excursion Report Form will be submitted for approval.

Study agents will be distributed according to standard pharmacy procedures. All drug products will be stored in a securely locked area, accessible only to authorized site personnel. To ensure the stability of the study drug and to ensure proper product identification, the drug products will not be stored in a container other than the container in which they are supplied. Consideration will be given to handling, preparation, and disposal through measures that minimize drug contact with the body. Appropriate precautions will be followed to avoid direct eye contact or exposure through inhalation when handling study drugs.

Records will be maintained indicating the receipt, dispensation, and destruction of all investigational product shipments. The responsible Pharmacist or designated staff at the investigational site must keep an accurate inventory of study product shipments received, the amount of study product administered, and all product returned or destroyed. This information is to be recorded on the Master Drug Accountability Log, as well as on the Investigational Product Overall Subject Accountability Log.

